7.3. Dose Adjustment Criteria

Dose modification will be allowed for subjects who experience an on-target AE considered to be treatment related that would otherwise lead to study or treatment discontinuation. The decision to reduce the dose of study drug will require consultation with the Investigator, the CRO's Medical Monitor, and the Sponsor's Chief Medical Officer. To preserve the study blind, the total number of combined tablets of study drug and matching placebo will remain the same. The subject's study drug assignment will NOT be unblinded. Dose modification is not allowed for subjects who have any of the TEAEs described in Section 8.3 that require permanent discontinuation. Additional details are provided in the Pharmacy Manual.

Dose interruptions may also be allowed (see also [Appendix A](#) and Section 8.3).

In the instance of a dose hold due to an AE or SAE, the decision to resume study drug will require consultation with the Investigator, the CRO's Medical Monitor, and the Sponsor's Chief Medical Officer.

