12.2.3. Recording Adverse Events

Each subject must be carefully monitored for the development of any AEs. This information should be obtained in the form of non-leading questions (e.g., “How are you feeling?”) and from signs and symptoms detected during each physical examination, observations on the part of study personnel, and spontaneous reports from subjects.

All AEs (serious and non-serious) spontaneously reported by the subject and/or in response to an open question from study personnel or revealed by observation, physical examination, or other diagnostic procedures will be documented in the subject’s source documents and recorded in the eCRF. Any clinically relevant (as determined by the Investigator) deterioration in laboratory assessments or other clinical findings is considered an AE and must be recorded in the subject’s source documents and in the eCRF.

Information about AEs will be collected from Screening (i.e., after the ICF is signed) through 28 days after the last dose of study drug. The AE term should be recorded in standard medical terminology when possible. Also, when possible, signs and symptoms indicating a common underlying pathology should be noted as one comprehensive event. For each AE, the Investigator will evaluate and report the onset date, resolution date, intensity, causality, action taken, serious outcome (if applicable), and whether or not it caused the subject to discontinue the study.

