13.3. Safety Analysis

Safety data will be evaluated for the Safety population (Section 13.4.2) on the basis of TEAEs, clinical laboratory assessments, vital signs, ECGs, weight, and physical examinations. Changes from Baseline in key clinical laboratory measurements, vital signs, physical examinations, and weight will be summarized by treatment group using standard descriptive statistics. A TEAE is defined as an AE that was not present prior to treatment with study drug but appeared following treatment or was present at treatment initiation but worsened during treatment. All AEs will be coded by preferred term using the Medical Dictionary for Regulatory Activities (MedDRA; current version) and NCI CTCAE (current version) grading.

TEAE incidence rates will be summarized using frequency and percentage for each treatment group and in total. TEAEs through 30 days after the last dose of study treatment will be

summarized by MedDRA (current version) system organ class and preferred term. AEs will also be summarized by NCI CTCAE grade and by causality (attribution to study treatment, related/not related to investigational medicinal product). Grades 3 and 4 AEs, SAEs, and AEs resulting in dose modification or treatment discontinuation will be summarized by preferred terms. Investigational medicinal product compliance and tolerability ratings will be summarized descriptively for each treatment group.

All safety data will be presented in data listings.

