An overview of TEAEs will be produced, including counts and percentages of subjects with any incidences of: TEAEs, TEAEs related to study treatment, serious adverse events (SAEs), TEAEs leading to study drug discontinuation, TEAEs with CTCAE grade 3 or higher, and fatal SAEs. The number of AEs will also be included in the summary.

In addition to the overview of TEAEs, the following summaries of AEs will be provided for the safety population by treatment group and overall:

- TEAEs by SOC and PT
- TEAEs related to study treatment by SOC and PT
- CTCAE Grade 3 or higher TEAEs by SOC and PT
- CTCAE Grade 3 or higher TEAEs related to study treatment by SOC and PT
- SAEs by SOC and PT
- TEAEs leading to treatment discontinuation by SOC and PT
- Skin and subcutaneous tissue disorders TEAEs by PT
- Eye disorder TEAEs by PT

Summaries of TEAEs by SOC, PT, and maximum severity as well as TEAEs by SOC, PT, and maximum relationship to study treatment will also be prepared.

Skin and subcutaneous tissue disorders and eye disorder TEAE summaries will also be performed for the mITT population.

A comprehensive listing of all AEs will be provided in a by-subject data listing. In addition, the following listings will be provided:

- TEAEs related to study treatment
- SAEs
- TEAEs leading to treatment discontinuation; and
- Fatal AEs.

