11. CHANGES TO THE PLANNED ANALYSES

The following changes were made to analyses specified in the protocol. Any additional changes to the planned analyses as detailed in this SAP will be described in the CSR.

- Co-primary objectives and endpoints were added.
- Added 'To evaluate the effect of TVB-2640 50 mg QD compared with matching placebo on resolution of steatohepatitis and no worsening of liver fibrosis (by NASH CRN fibrosis score). Resolution of steatohepatitis is defined as absence of fatty liver disease or isolated or simple steatosis without steatohepatitis and a NAS of 0 or 1 for inflammation, 0 for ballooning, and any value for steatosis at Week 52.' as a secondary objective and endpoint.
- Added 'To evaluate the effect of TVB-2640 50 mg QD compared with matching placebo on histological improvement (decrease) at Week 52 in NAS by ≥ 2 points.' as a secondary objective and endpoint.
- Removed 'To evaluate the effect of TVB-2640 50 mg QD compared with matching placebo on fibrosis as assessed by ≥ 1 stage of fibrosis improvement by NASH CRN score without worsening of NAS (defined as no increase in any component of NAS) at Week 52.' as a secondary objective and endpoint.
- Added proportion of MRI-PDFF $\geq 50\%$ responders, MELD, and Agile3+ endpoints.
- Region (North America or not North America) was removed as an effect in all analyses.

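### The SAP leaves out the protocol's summary of adverse events leading to dose modification and does not record the omission

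*SAP*

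**What the plan says.** Protocol Section 13.3 states the safety commitment: "Grades 3 and 4 AEs, SAEs, and AEs resulting in dose modification or treatment discontinuation will be summarized by preferred terms".

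Protocol Section 7.3 opens dose modification to a subject with an "on-target AE considered to be treatment related that would otherwise lead to study or treatment discontinuation". Section 9.5 defines the step-down as 50 mg to 25 mg, with a sham adjustment for placebo subjects (new bottles, same tablets) to keep the blind. Section 7.3 then mentions dose interruptions as a separate possibility. For each AE, Protocol Section 12.2.3 has the investigator "report the onset date, resolution date, intensity, causality, action taken", among other items.

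In SAP Section 10.1 the overview includes "TEAEs leading to study drug discontinuation, TEAEs with CTCAE grade 3 or higher, and fatal SAEs", and the table list includes "TEAEs leading to treatment discontinuation by SOC and PT". On listings it says "A comprehensive listing of all AEs will be provided in a by-subject data listing", followed by separate listings for related TEAEs, SAEs, TEAEs leading to discontinuation, and fatal AEs. Nothing in the section refers to dose modification, reduction or interruption.

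SAP Section 8.7 summarises mean daily dose and total cumulative dose, and promises listings of planned and actual treatment and of exposure. SAP Section 11 opens with "The following changes were made to analyses specified in the protocol" and gives six bullets.

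**The concern.** Safety and tolerability of 50 mg once daily is a primary objective in both documents (Protocol Section 6.1.1, SAP Section 3.1). The protocol planned to show two outcomes of poor tolerability side by side: events that ended treatment and events that changed the dose. The SAP keeps only the first.

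The two are linked by design, because the protocol offers a dose change as an alternative to stopping. When it succeeds, the event does not reach the discontinuation table. A reader of the SAP's tables would see how many subjects stopped because of an event. They would not see how many stayed on study only after a reduction, or which events prompted it. That information is needed to judge 50 mg for later trials. Because the removal is not declared, nobody comparing the final report with the SAP would know that a protocol analysis had been dropped.

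**Working it through.** No arithmetic applies. The check sets the two documents side by side and then traces one event through the planned outputs.

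**Step 1. Match the protocol's categories to the SAP's tables.** Protocol Section 13.3 names four groups of events in one sentence.

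| Protocol 13.3 | SAP 10.1 overview | SAP 10.1 table by SOC and PT |
|---|---|---|
| Grades 3 and 4 AEs | yes (Grade 3 or higher) | yes (Grade 3 or higher) |
| SAEs | yes | yes |
| AEs leading to treatment discontinuation | yes | yes |
| AEs resulting in dose modification | no | no |

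Three of the four are carried over. The fourth appears in no overview row, table or dedicated listing.

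**Step 2. Trace an event.** Take a subject on 50 mg with an event judged on-target and drug-related that would have ended treatment, who is stepped down to 25 mg and continues.

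- The event is counted in all TEAEs, related TEAEs, and the tables by maximum severity and maximum relationship. It is also counted in the Grade 3 or higher, SAE, skin or eye tables if it meets those definitions.
- The event is in the comprehensive by-subject AE listing.
- It is absent from the discontinuation overview row, table and listing, which are the only outputs defined by the action taken.
- Exposure duration in SAP Section 8.7 is stop date minus start date plus 1, so a step-down does not alter it and a hold is not subtracted. Mean daily and cumulative dose can reflect a reduction, but these summaries are not tied to an event.

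**Step 3. Check disclosure.** The six bullets in SAP Section 11 cover the co-primary endpoints, two added secondary endpoints, one removed fibrosis endpoint, the added 50% MRI-PDFF, MELD and Agile 3+ endpoints, and the removal of region. None concerns adverse events. That section also defers further changes to the clinical study report, but this difference between the SAP and the protocol already exists and could be declared now.

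**Step 4. Look for a size.** An estimate of the affected events needs a step-down rate at 50 mg, ideally by arm. Neither document gives one, from this trial or from the earlier study summarised in Protocol Section 5.2. No number can be derived.

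**The case against.** The strongest reply is that only a label is missing. The events remain in the general, related, severity, skin and eye tables, and the skin and eye summaries are repeated in the mITT population. AE listings and exposure listings are both by subject, so a step-down can be matched to its event by hand. This is correct and limits the point: what is missing is a tabulation, not the data. A reader might infer that discontinuation is the only tolerability output left, but the documents do not support that. It is the only output defined by the action taken.

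A second reply is that Section 7.3 uses dose modification mainly for a reduction and names interruptions separately. This also stands. Only reductions are clearly within the dropped commitment. A table of interruptions is a sensible addition, not a restoration. Nor does a hold show that a subject failed on 50 mg, because Protocol Section 8.3 lets study drug resume after mild to moderate palmar-plantar erythrodysesthesia (PPE) resolves.

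A reader might try to size the gap from the earlier study's China cohort, where 3 of 21 subjects on 50 mg had PPE, by applying the interruption instruction in Section 8.3 and scaling to the 108 planned active subjects. The documents do not support this. The figure is a 12-week incidence of an event, not of dose changes. The same paragraph of Section 5.2 reports that all TEAEs in that cohort resolved without dose adjustment. Among the 68 treated US subjects (25 mg or 50 mg), PPE is not among the most common events listed. The calculation would also count holds, which the commitment does not clearly cover.

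A reader might further infer that the missing events fall mainly in the active arm. That is plausible, but no figure supports it, and placebo subjects can receive blinded adjustments too.

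Finally, safety is analysed descriptively, no efficacy conclusion changes, and the synopsis does not mention the dose-modification summary. All true, but Section 13.3 states the commitment in plain terms and it bears on a primary objective.

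**Conclusion.** The point holds in a narrow form. A safety summary specified in Protocol Section 13.3 is half missing from SAP Section 10.1, and SAP Section 11 does not say so. Events managed by step-down are counted elsewhere but are not identified in any table as having led to a dose change. The planned tables therefore give an incomplete answer on the tolerability of 50 mg.

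The size is unknown and cannot be estimated from the documents. The conclusion rests on the text comparison alone and would stand whether few or many subjects were stepped down. It assumes that the outputs named in SAP Section 10.1 are the full set planned. This is a correction that should be made before unblinding. It is not a threat to the trial's efficacy conclusions.

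**What to change.** In SAP Section 10.1, restore the protocol summary. Add an overview row and a table by SOC and PT, by arm, of TEAEs leading to dose modification (reduction), derived from the action taken recorded for each AE.

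Two additions go beyond strict restoration and are worth making:

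- A separate row and table for TEAEs leading to study drug interruption, where the recorded action taken distinguishes it. The CRF is not among the documents, so this needs checking.
- The number of subjects in each arm with a dose adjustment, counting blinded placebo adjustments, so that the arms can be compared on the same footing.

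If the removal was intended, state it in SAP Section 11 with the reason.

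The protocol already requires action taken to be reported, so no new data collection is needed for the reduction table. The cost is SAP wording and a few extra descriptive tables. The reported tolerability of 50 mg may look less favourable as a result.

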10.2. Clinical Laboratory Evaluations

Clinical chemistry, hematology, coagulation, and urinalysis parameters will be reported based on conventional units as applicable. The following laboratory evaluations will be reported in data summaries:

- Chemistry: Chloride, Sodium, Blood urea nitrogen, Creatinine, Albumin, Total protein, AST, GGT, Total bilirubin, Indirect and direct bilirubin, Carbon dioxide, Potassium, Calcium, Magnesium, Glucose, Alkaline phosphatase, ALT, Creatine phosphokinase (total and fractionated) (screening and baseline only). Note that AST and ALT collected as part of the clinical chemistry panel are also applicable for efficacy assessments.
- Hematology: Hematocrit, Hemoglobin, Red blood cell count, MCV, Platelet count, White blood cell count with differential, Absolute neutrophil count, MCHC.
- Coagulation Studies: Prothrombin time, Fibrinogen, Activated partial thromboplastin time, international normalized ratio (INR).
- Urinalysis: Specific gravity, Protein, pH, Ketones, Blood, Microscopic examination of sediment, Glucose.

Observed values and changes from baseline for laboratory evaluations will be summarized at each visit and will also include the most extreme change from baseline. The percent change from baseline at each visit and the most extreme percent change from baseline will also be summarized. Select laboratories mean change from baseline by study visit will be depicted graphically in a longitudinal line plot with standard error of the mean.

Laboratory data will also be summarized in shift tables of baseline to most extreme change based on range categories of low (below lower limit of normal [LLN], normal, and high [above upper limit of normal [ULN]]. Urinalysis results and shifts will be based on the categories present in the data.

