8.2. Subject Exclusion Criteria

Subjects meeting any of the following criteria are not eligible for enrollment into the study.

1. History of harmful alcohol intake for a period of more than 3 consecutive months within 1 year prior to Screening in the judgement of the Investigator.
2. Active substance abuse, including inhaled or injected substances (cocaine and other illegal/banned substances; any opiate, amphetamine, or benzodiazepine for which the subject does not have an existing prescription), within 1 year prior to Screening (note that recreational cannabis/tetrahydrocannabinol use is permissible).
3. Patient-reported or medically documented gain or loss of >5% of body weight in the 6 months prior to Baseline (Day 1) or >10% of body weight in the 12 months prior to Screening.
4. Prior or planned (during the study period) bariatric surgery that may interfere with study drug absorption (e.g., roux-en-Y gastric bypass); gastroplasty and gastric reduction surgery are acceptable.
5. Type 1 diabetes mellitus by history.
6. Positive SARS-CoV-2 polymerase chain reaction (PCR) test within 30 days prior to the Baseline (Day 1) visit date or history of hospitalization for COVID-19 <6 months prior to the Screening visit date. Note that previous COVID-19 infection alone is not exclusionary, and COVID-19 vaccination is allowed. Infection and/or vaccination must be documented as medical history and/or concomitant medication, respectively.
7. Known positivity for HIV infection or positive HIV antibody result at Screening.
8. Positive hepatitis B virus antigen (HBsAg) result at Screening.
9. Positive hepatitis C virus (HCV) RNA test at Screening; however, subjects with chronic HCV infection and liver disease who were treated with anti-HCV therapy and achieved a sustained virologic response at least 2 years prior to Screening are not prevented from study participation.
10. Uncontrolled T2DM, defined as HbA1c >9.5% at Screening.
11. Serum LDL-C concentration at Screening >190 mg/dL, and the subject has been taking LDL-C-lowering treatment for \geq 30 days prior to Screening.
12. ALT and/or AST result $>5 \times$ the upper limit of normal (ULN) at Screening. One repeat test may be allowed within 7 days of receipt of the result at the discretion of the Investigator.
13. Alkaline phosphatase (ALP) result $\geq 2 \times$ ULN at Screening.

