APPENDIX A. ALGORITHM FOR EVALUATING SUBJECTS FOR POTENTIAL DRUG-INDUCED LIVER INJURY

During the study, aminotransferase elevations are to be managed as follows:

1. Isolated aminotransferase elevation (i.e., total bilirubin - normal):

ALT or AST	Event during the study	Action
Baseline ALT and AST within normal range	Increase $\geq 5 \times$ ULN	Repeat liver profile (AST, ALT, bilirubin) and PT/INR within 2 to 3 business days from the date results are received for review. Monitor the subject as per “close observation” definition* in the DILI guidance.
ALT or AST above normal range at Baseline	Increase $\geq 3 \times$ Baseline result, but no liver related symptoms (e.g., anorexia, nausea, vomiting, right upper quadrant pain, pruritus, cholestasis)	Interrupt study drug for at least 15 days. Initiate potential DILI evaluation for alternative etiologies, and repeat liver profile and PT/INR within 2 to 3 business days from the date results are received for review, and place subject under “close observation” as defined in the DILI guidance.
ALT or AST above normal range at Baseline	Increase $\geq 3 \times$ Baseline result, and subject experiences liver- related symptoms (e.g., anorexia, nausea, vomiting, right upper quadrant pain, pruritus, cholestasis)	Interrupt study drug for at least 15 days. Initiate potential DILI evaluation for alternative etiologies, and repeat liver profile and PT/INR within 2 to 3 business days from the date results are received for review, and place subject under “close observation” as defined in the DILI guidance.

Abbreviations: ALP = alkaline phosphatase; ALT = alanine aminotransferase; AST = aspartate aminotransferase; DILI = drug-induced liver injury; GGT = gamma-glutamyltransferase; INR = international normalized ratio; PT = prothrombin time; ULN = upper limit of normal.

*Close observation as defined in the FDA DILI guidance (i.e., laboratory testing and physical examination 2 to 3 times per week. Study drug is to be restarted only if a firm alternative etiology is “identified” and the liver tests return to ‘baseline’ levels).

Note the following:

The ‘baseline’ result for any laboratory parameter is the average of the Screening visit result, the Day 1 visit result and any unscheduled visit that occurred during the Screening period.’

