7. GENERAL DATA HANDLING CONSIDERATIONS

All analyses will be conducted using SAS software Version 9.4 or higher.

All data in the database will be presented in by-subject data listings. Unless otherwise stated, all listings will be sorted by treatment group, center ID, subject number, and assessment date and time, if available.

Unless stated otherwise, continuous data will be summarized by treatment group using descriptive statistics including number of subjects (n), mean, median, standard deviation (SD), first quartile (Q1), third quartile (Q3), minimum (min) value, maximum (max) value.

Unless stated otherwise, categorical data will be summarized by treatment group using counts and percentage based on the number of non-missing values. For selected summaries, the number of missing values will be presented as a separate category with no percentage, if one or more subjects have missing data. Counts of zero will be presented without percentages.

Descriptive statistics will be presented with the following numerical precision:

- Minimum and Maximum: same as the raw data collected
- Mean, Median, Q1, and Q3: one additional decimal place to that reported for Minimum and Maximum
- SD: two additional decimal places than the Minimum and Maximum
- Percentages: reported to one decimal place if percent is <100. If the value is 100, no decimal place will be reported.

Unless otherwise noted, statistical inference will be based on two-sided testing with a 5% significance level. Confidence intervals will be at the 90% and 95% levels.

P-values will be reported to four decimal places. If the value is below 0.0001 it will be noted as < 0.0001; if the value above 0.9999 it will be noted as > 0.9999.

All data up to the time of study completion/withdrawal from the study will be included in the analysis, regardless of duration of treatment.

Numbering for data displays will be based on [International Council for Harmonization \(ICH\) E3](#) whenever possible.

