7.9. Multiple Assessments and Visit Windows

Nominal visits (e.g., those identified by the study eCRF) will be the basis of summarization and statistical analysis; no visit date windowing will be conducted. Unless specified otherwise, data from unscheduled visits will be included in: (1) summaries of most extreme and baseline data, (2) summaries of specific abnormalities at any time post-baseline, (3) adverse events and any other summaries not based on study visit, (4) subject data listings, and (5) analyses that utilize MRI-PDFF, PK, lipidomic/metabolic biomarkers, collagen/fibrous area and fibrosis score assessed by digital pathology, SNPs relevant for NASH, and PRO-C3 data where unscheduled visit results may be used in analyses at the closest scheduled visit; if the closest scheduled visit already has valid MRI-PDFF data then the unscheduled visit results will not be used in the analysis.

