9.2. Secondary Efficacy Endpoints and Analyses

Secondary efficacy analyses for the other histological responder endpoints will be analyzed in the ITT and mITT populations using the methods described for the primary efficacy endpoint.

Secondary efficacy analyses of endpoints expressed as percent change or change from Baseline only at Week 26 or only at Week 52 will be analyzed in the ITT analysis set using an analysis of covariance (ANCOVA) model with fixed effects for T2DM status at baseline (Yes, No) and treatment group, and a covariate term for baseline analysis value of response. Least squares (LS) means for the percent change from Baseline by treatment and the associated standard errors, the

LS means for the difference between treatment groups, and the associated two-sided 95% CIs and two-sided p-values, based on t-tests, will be derived from the ANCOVA model.

For secondary endpoints assessed at multiple visits, a linear mixed-effects model for repeated measures (MMRM) may be used. The model will include T2DM status at baseline (Yes, No), treatment group, visit, and treatment-by-visit interaction as the fixed effects, and baseline value as a covariate, and the model will use an unstructured variance-covariance matrix. The point estimates for the least-squares mean of the difference treatment groups at each visit and the corresponding 95% confidence interval and two-sided p-value will be summarized. If convergence problems arise when fitting the model, a spatial power covariance structure will be used as a first step. If the model still has convergence issues, compound symmetry covariance structure will be employed. The Kenward-Roger correction for the denominator degrees of freedom will be applied.

ALT, AST, ALP, and GGT will also be summarized in shift tables of baseline to each visit based on range categories of low (below lower limit of normal [LLN], normal, and high [above upper limit of normal [ULN]]).

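### SAP 10.2 gives the most extreme laboratory change no direction, and no laboratory table counts ALT, AST or bilirubin rises by multiples of ULN or Baseline

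*SAP*

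**What the plan says.** SAP 10.2 specifies several laboratory displays. The first is by visit: "Observed values and changes from baseline for laboratory evaluations will be summarized at each visit and will also include the most extreme change from baseline". Percent change is treated the same way, and selected analytes are plotted. The shift table comes after these: "Laboratory data will also be summarized in shift tables of baseline to most extreme change based on range categories of low", normal and high.

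SAP 9.2 adds a second shift table for the liver enzymes: "ALT, AST, ALP, and GGT will also be summarized in shift tables of baseline to each visit based on range categories of low", normal and high, so the categories are the same three. Bilirubin is not in that table.

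SAP 7 says continuous summaries include "first quartile (Q1), third quartile (Q3), minimum (min) value, maximum (max) value", and that all data are listed by subject. SAP 7.9 works on nominal visits. It brings unscheduled results into "summaries of most extreme and baseline data" and into any-time abnormality summaries, but routine chemistry is not among the analyses where an unscheduled result may stand in for a scheduled visit. SAP 10.2 defines no abnormality threshold.

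On the Protocol side, exclusion criterion 12 (Section 8.2) turns a subject away only when ALT or AST exceeds 5 times "the upper limit of normal (ULN) at Screening. One repeat test may be allowed within 7 days". Criterion 14 caps total bilirubin at 1.3 mg/dL, apart from Gilbert's syndrome. Appendix A has separate rows for subjects with "ALT or AST above normal range at Baseline", where the event is a rise to at least 3 × Baseline. For normal baselines the event is at least 5 × ULN. The combined row needs bilirubin above 2 mg/dL plus an aminotransferase at 3 × Baseline or 5 × ULN, whichever comes first.

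**The concern.** There are two separate weaknesses.

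- **Categories.** This population may enter with raised liver enzymes, and once a subject starts above ULN every further rise stays in the High category. The shift tables in 10.2 and 9.2 then cannot tell a stable raised ALT from a rise that Appendix A treats as possible liver injury.
- **Direction.** A most extreme change can be a fall or a rise. SAP 10.4 solves this for ECG with a worst-observed-value rule, and 10.5 uses a worst-case summary for eye findings. The laboratory section has no equivalent, although ALT, AST and GGT are also analysed as efficacy endpoints. If the programmer takes the largest absolute change, an improvement at one visit can displace a rise at another.

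Safety and tolerability are a primary objective, and the Protocol gives liver injury its own appendix. A reader of the report would expect to see how many subjects per arm had a hepatic elevation of a given size, and no planned laboratory table says so.

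**Working it through.** The plan states no figure to reproduce here, so the check is on logic. ALT and AST are in multiples of ULN. The subject values are examples, not data from the trial.

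**Step 1: what the three categories can show.**

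| Baseline | Post-baseline | Peak ÷ Baseline | Cell |
|---|---|---|---|
| 2 | 2 | 1 | High-to-High |
| 2 | 6 | 3 | High-to-High |
| 2 | 10 | 5 | High-to-High |
| 0.8 | 1.1 | 1.38 | Normal-to-High |
| 0.8 | 5 | 6.25 | Normal-to-High |

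The second and third rows reach 3 × Baseline and the last reaches 5 × ULN. Each shares a cell with a subject who has no change or a trivial one. This holds under any reading of most extreme, and also in the by-visit table of 9.2.

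**Step 2: when a fall displaces a rise.** Assume the largest absolute change is meant. Let B be baseline, L the lowest and P the highest post-baseline value. The fall is selected when B − L > P − B, that is, when P < 2B − L. Since L cannot be negative, P must lie below 2B.

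- *At least 3 × Baseline:* the rise is at least 2B and the fall at most B. It is never hidden.
- *At least 5 × ULN from a normal baseline:* the rise is at least 5 − 1 = 4 and the fall at most 1. It is never hidden.
- *5 × ULN in the combined row, raised baseline:* hiding needs B > 5 − B, so B > 2.5. With entry capped at 5, the range is 2.5 to 5 × ULN.
- *Bilirubin just above 2 mg/dL:* hiding needs B > 2 − B, so B > 1.0 mg/dL. The entry limit of 1.3 allows this.

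**Step 3: examples.**

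| B | L | P | Fall | Rise | Cell, largest absolute change | Cell, maximum value |
|---|---|---|---|---|---|---|
| 3 | 0.9 | 5 | 2.1 | 2.0 | High-to-Normal | High-to-High |
| 4.5 | 0.9 | 7 | 3.6 | 2.5 | High-to-Normal | High-to-High |
| 4.5 | 1.5 | 7 | 3.0 | 2.5 | High-to-High | High-to-High |

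For bilirubin, baseline 1.3, lowest 0.5 and highest 2.05 mg/dL give a fall of 0.80 against a rise of 0.75, so the fall is selected.

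The last column shows that moving to the maximum cures the direction problem but not the category problem. Separating these subjects needs multiples of ULN or of Baseline.

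**Step 4: which baseline.** Appendix A averages the Screening, Day 1 and unscheduled screening results. SAP 7.6 takes the last value before dosing. For a subject with Screening 3 and Day 1 2 × ULN and no other result, 3 × Baseline is 3 × 2.5 = 7.5 × ULN under Appendix A and 3 × 2 = 6 × ULN under the SAP. A threshold table must say which it uses.

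**The case against.** The strongest reply is that the shift table is an additional display and the signal appears elsewhere. Observed values, changes and percent changes are shown by visit with minimum and maximum. The most extreme percent change takes in unscheduled results. A fall cannot exceed 100%, so a rise to 3 × Baseline (+200%) is always the value selected for that subject and feeds the arm's maximum. Every value is listed. Abnormalities that the investigator judges clinically significant become adverse events, tabulated by preferred term and grade. SAP 7.9 anticipates summaries of specific abnormalities, table shells are not among the documents, and safety is descriptive, so tables can be added later at no cost in type I error.

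Most of that stands. It rules out the inference that a liver-injury rise would vanish from the report. Three limits remain. An arm's maximum shows one subject and gives no count and no concurrent bilirubin. The by-visit tables omit the unscheduled repeat tests that Appendix A calls for. The adverse-event route depends on the investigator's judgement, and SAP 10.1 plans dedicated skin and eye tables but none for the liver.

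A reader might also infer that masking is heavier on active drug because ALT falls there. SAP 7.4 tests the ALT endpoint two-sided with no stated direction. The documents also do not give the baseline ALT distribution, the expected fall or the visit-to-visit variability. No rate of masking, and no share of subjects starting High, can be derived from them.

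**Conclusion.** The point holds as a gap in specification and counting, and it is worth correcting. The category weakness is certain for any subject above ULN at baseline and depends on no reading of the text. The direction weakness is conditional on the largest-absolute-change reading and is bounded: only peaks below 2 × Baseline can be displaced. A reader might infer that an ALT fall could conceal an isolated-aminotransferase trigger; Step 2 of the working shows that it cannot. What it can displace is the 5 × ULN component of the combined trigger for baselines of 2.5 to 5 × ULN, and a bilirubin rise just above 2 mg/dL for baselines above 1.0 mg/dL. How many subjects would be affected is unknown. The consequence is that a primary safety objective lacks a by-arm laboratory count of hepatic elevations, although the underlying values are collected and reported in other forms.

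**What to change.** In SAP 10.2, replace the shift to most extreme change with two shifts per analyte: to the maximum and to the minimum post-baseline value, each including unscheduled results.

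Add a by-arm table that counts subjects whose maximum ALT, AST and bilirubin reach stated multiples of ULN and of Baseline. This is the essential part, because shifts to the maximum still leave High-to-High unresolved. In the same table, count subjects who meet the laboratory part of each Appendix A criterion with its conditions kept:

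- at least 5 × ULN, for a normal baseline;
- at least 3 × Baseline, for a raised baseline;
- bilirubin above 2 mg/dL together with the aminotransferase criterion, or with the ALP or GGT criterion;
- bilirubin above 2 mg/dL or INR of at least 1.5, only with the symptoms or immunological signs that the row requires.

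Dropping those conditions would miscount. For example, a subject going from 4.5 to 5 × ULN would be an event if the 5 × ULN rule were applied regardless of baseline.

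State whether Baseline is the Appendix A average or the SAP 7.6 last pre-dose value. The cost is SAP wording and a few more tables, with no new data.
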